6.4 Criteria for premature discontinuation of trial product

The patient may be prematurely discontinued from trial product at the discretion of the investigator due to a safety concern.

The patient must be prematurely discontinued from trial product if the following applies:

1. Included in the trial in violation of the inclusion and/or exclusion criteria
2. Simultaneous participation in another clinical trial of an approved or non-approved investigational medicinal product.
3. Incapacity or unwillingness to follow the trial procedures
4. Anaphylactic reaction
5. Thromboembolic event
6. Event of disseminated intravascular coagulation (DIC)
7. Development of inhibitors to Factor VIII (≥ 0.6 BU)
8. Lack of efficacy due to neutralising antibodies towards concizumab
9. Lack of efficacy defined as ≥ 3 treated sBEs within the previous 12 weeks in patients being treated with the highest dose level (0.25 mg/kg) of concizumab.

See Section [8.1.4](#) for procedures to be performed for patients discontinuing trial product prematurely.

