8.3 Efficacy assessments

8.3.1 Bleeding episodes

All bleeding episodes treated with FVIII and symptoms related to the underlying disease must be captured in the eDiary by the patient or in the eCRF by the investigator. The trial site should be informed of the details of all bleeding episodes, including those that are treated outside of the trial site. All information captured including severe bleeding episodes, during visits at the trial site will be collected in the eCRF.

When home treatment is initiated at visit 2 all bleeding episodes and injections with concizumab and turoctocog alfa (rFVIII) infusions occurring outside the trial site should be entered in the eDiary by the patient (Section [8.6.2.3](#)). The completed eDiary is considered source data.

The following must be recorded for any bleeding episode, including bleeding episodes that do not require treatment with rFVIII (turoctocog alfa):

- Start date and time
- Stop date and time (see [Table 8–1](#) for definition)
- Anatomical location(s)
 - Position (left/ right)
- Cause (see [Table 8–2](#) for definitions)
 - spontaneous
 - traumatic
 - post-surgical
- Severity (see [Table 8–3](#) for definitions)

Protocol
 Trial ID:NN7415-4255
 UTN:U1111-1179-3872
 EudraCT no.:2016-000614-29

~~CONFIDENTIAL~~

Date: 05 May 2017
 Version: 2
 Status: Final
 Page: 55 of 124

Novo Nordisk

- mild/moderate, severe
 - classification and of severe bleeding episodes is the responsibility of the investigator
- Treatment, if any
 - rFVIII (turoctocog alfa) administration(s) or other product administrations
 - dose, date, time
 - other medicinal treatments related to the bleeding episode (e.g. pain relieving medication, non-medical therapy etc.)
 - record as concomitant medication (see Section [8.2.3](#))
- Symptoms during bleeding episodes
 - Pain
 - Blood in urine
 - Tingling sensation
 - Swelling
 - Mouth/Gum bleed
 - Warmth
 - Loss of movement
 - Bruises
 - Nose bleed

Only report the bleeding episode as an AE/SAE if fatal, life threatening or evaluated as related to trial product (see section [12.1](#))

Table 8–1 Definition of stop of bleeding episode

Stop time is:	When the patient experiences/observes signs of cessation of the active bleeding episode such as; pain relief, no increase in swelling/limitation of motion and improvement in other objective signs of the bleeding episode
Stop time is not:	When pain and objective signs of the bleeding episode are completely resolved

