Table 8–2 Definitions of bleeding episodes (cause of bleed)

Category	Definition
Spontaneous	Not linked to a specific, known action or event
Traumatic	Caused by a specific, known action or event (e.g. injury or exercise)

Protocol
 Trial ID:NN7415-4255
 UTN:U1111-1179-3872
 EudraCT no.:2016-000614-29

~~CONFIDENTIAL~~

Date: 05 May 2017
 Version: 2
 Status: Final
 Page: 56 of 124

Novo Nordisk

Post-surgical	Bleeding episodes after surgery from the surgical wound. Bleeding episodes during surgery does not fall under this category
---------------	---

Table 8–3 Definition of bleeding episode severity and treatment recommendation

Category	Definition	Treatment recommendation
Mild/Moderate	
Examples: uncomplicated musculoskeletal bleeding episodes (joint, muscular bleeds without compartment syndrome), mucosal- or subcutaneous bleeding episodes
 
Mild/moderate bleeding episodes may occur in other anatomical locations
	Mild/moderate bleeding episodes can be treated at home before contact to the investigator
Severe	
Examples: intracranial, retroperitoneal, iliopsoas and internal neck bleeding episodes; muscle bleeding episodes with compartment syndrome; bleeding episodes associated with a significant decrease in the haemoglobin level (>3g/dl)
 
Severe bleeding episodes may occur in other anatomical locations
 
Bleeding episodes that require hospitalisation
 
All life-threatening bleeding episodes
	Severe bleeding episodes must be treated immediately
Instruction for patients	The patient must be instructed to contact the investigator immediately if in doubt regarding treatment of a bleeding episode and to discuss what other actions may need to be taken	

Information about bleeding episodes prior to visit 2 will be recorded in eCRF.

The trial site should be informed of the details of all bleeding episodes, including those that are treated outside of the trial site. After visit 2 bleeding episodes must be recorded either in the eDiary (if treated at home) or in the eCRF (if treated at the trial site), see section [12.3](#).

Severity of bleeding episodes must be evaluated by the investigator according to [Table 8–3](#) and reported in the eDiary database.

Prophylactic treatment with concizumab should continue independent of bleeding episodes and their treatment, i.e. the original dosing schedule should be maintained unless investigator judges

Protocol
 Trial ID:NN7415-4255
 UTN:U1111-1179-3872
 EudraCT no.:2016-000614-29

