12.1.6 Adverse event of special interest

An adverse event of special interest (AESI) is an event, which in the evaluation of safety, has a special focus. In this trial, the following AEs fulfil the AESI criteria:

- Thromboembolic events including but not limited to,
 - disseminated intravascular coagulation (DIC) (A),
 - clinical signs or laboratory indications of arterial and venous thrombosis including myocardial infarction (B),
 - pulmonary embolism (C),
 - stroke (D),
 - deep vein thrombosis (E),
 - other clinically significant thromboembolic events (F) and peripheral artery occlusion (see below G), see definitions below.

The AESIs must be reported on an AE form and a safety information form.

Protocol
 Trial ID:NN7415-4255
 UTN:U1111-1179-3872
 EudraCT no.:2016-000614-29

~~CONFIDENTIAL~~

Date:	05 May 2017	Novo Nordisk
Version:	2	
Status:	Final	
Page:	83 of 124	

A) Definition of disseminated intravascular coagulation (DIC), as defined below:

The definition of DIC in this trial should be made according to the International Society on Thrombosis and Haemostasis (ISTH) criteria. Thus, a DIC diagnosis may be based on clinical signs and symptoms of a bleeding tendency or thrombotic tendency, organ dysfunction and the laboratory parameters criteria as listed below:

- Platelet count ($>100 \times 10^9/L = 0$, $<100 \times 10^9/L = 1$, $<50 \times 10^9/L = 2$)
- Elevated D-dimer (no increase = 0, moderate increase = 2, strong increase = 3)
- Prolonged PT ($<3 \text{ s} = 0$, $>3 \text{ but } <6 \text{ s} = 1$, $>6 \text{ s} = 2$)
- Fibrinogen level ($>1 \text{ g/L} = 0$, $<1 \text{ g/L} = 1$)
- Calculate score: ≥ 5 compatible with overt DIC

(B) Myocardial infarction is defined according to the “Third Universal Definition of Myocardial Infarction”²⁴

Criteria for acute myocardial infarction - The term acute myocardial infarction (MI) should be used when there is evidence of myocardial necrosis in a clinical setting consistent with acute myocardial ischemia. Under these conditions any one of the following criteria meets the diagnosis for MI:

- Detection of a rise and/or fall of cardiac biomarker values [preferably cardiac troponin (cTn)] with at least one value above the 99th percentile upper reference limit (URL) and with at least one of the following:
 - Symptoms of ischemia.
 - New or presumed new significant ST-segment–T wave (ST–T) changes or new left bundle branch block (LBBB).
 - Development of pathological Q waves in the ECG.

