 - Imaging evidence of new loss of viable myocardium or new regional wall motion abnormality.
 - Identification of an intracoronary thrombus by angiography or autopsy.

Criteria for prior myocardial infarction- Any one of the following criteria meets the diagnosis for prior MI:

- Pathological Q waves with or without symptoms in the absence of non-ischemic causes. Imaging evidence of a region of loss of viable myocardium that is thinned and fails to contract, in the absence of a non-ischemic cause.
- Pathological findings of a prior MI.

Recurrent myocardial infarction - Incident MI’ is defined as the individual’s first MI. When features of MI occur in the first 28 days after an incident event, this is not counted as a new event for epidemiological purposes. If characteristics of MI occur after 28 days following an incident MI, it is considered to be a recurrent MI.

C) Definition of pulmonary embolism:

Protocol
 Trial ID:NN7415-4255
 UTN:U1111-1179-3872
 EudraCT no.:2016-000614-29

~~CONFIDENTIAL~~

Date:	05 May 2017	Novo Nordisk
Version:	2	
Status:	Final	
Page:	84 of 124	

The “Clinical Practice Guideline from the American Academy of Family Physicians and the American College of Physicians” on diagnosis of venous thromboembolism recommends diagnostic imaging studies for patients with intermediate or high pre-test probability of pulmonary embolism²⁵.

Accordingly, the definition of pulmonary embolism is the following: obstruction of a pulmonary artery or one of its branches, most frequently by detached fragments of thrombus from a leg or pelvic vein, diagnosed by at least one of the following:

- Positive findings in ventilation/perfusion scan
- Positive findings in a spiral (helical) computerised tomography (CT) or angiography
- Positive findings in a magnetic resonance imaging (MRI)
- Positive findings in a pulmonary angiography

D) Definition of stroke:

The definition of central nervous infarction is according to the American Heart Association/American Stroke Association Expert Consensus Document: “An Updated Definition of Stroke for the 21st Century”²⁶.

Accordingly, the term “stroke” should be broadly used to include all of the following:

Definition of central nervous system (CNS) infarction: CNS infarction is brain, spinal cord, or retinal cell death attributable to ischemia, based on:

- 1. pathological, imaging, or other objective evidence of cerebral, spinal cord, or retinal focal ischemic injury in a defined vascular distribution; or

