- 2. clinical evidence of cerebral, spinal cord, or retinal focal ischemic injury based on symptoms persisting 24 hours or until death, and other etiologies excluded.

Note: CNS infarction includes haemorrhagic infarctions, types I and II; see “Haemorrhagic Infarction”.

Definition of ischemic stroke: An episode of neurological dysfunction caused by focal cerebral, spinal, or retinal infarction. Note: Evidence of CNS infarction is defined above.

Definition of silent CNS infarction: Imaging or neuropathological evidence of CNS infarction, without a history of acute neurological dysfunction attributable to the lesion.

Definition of intracerebral haemorrhage: A focal collection of blood within the brain parenchyma or ventricular system that is not caused by trauma. Note: Intracerebral haemorrhage includes parenchymal haemorrhages after CNS infarction, types I and II - see “Haemorrhagic Infarction”.

Definition of stroke caused by intracerebral haemorrhage: Rapidly developing clinical signs of neurological dysfunction attributable to a focal collection of blood within the brain parenchyma or ventricular system that is not caused by trauma.

Protocol
 Trial ID:NN7415-4255
 UTN:U1111-1179-3872
 EudraCT no.:2016-000614-29

~~CONFIDENTIAL~~

Date:	05 May 2017	Novo Nordisk
Version:	2	
Status:	Final	
Page:	85 of 124	

Definition of silent cerebral haemorrhage: A focal collection of chronic blood products within the brain parenchyma, subarachnoid space, or ventricular system on neuroimaging or neuropathological examination that is not caused by trauma and without a history of acute neurological dysfunction attributable to the lesion.

Definition of subarachnoid haemorrhage: Bleeding into the subarachnoid space (the space between the arachnoid membrane and the pia mater of the brain or spinal cord).

Definition of stroke caused by subarachnoid haemorrhage: Rapidly developing signs of neurological dysfunction and/or headache because of bleeding into the subarachnoid space (the space between the arachnoid membrane and the pia mater of the brain or spinal cord), which is not caused by trauma.

Definition of stroke caused by cerebral venous thrombosis: Infarction or haemorrhage in the brain, spinal cord, or retina because of thrombosis of a cerebral venous structure. Symptoms or signs caused by reversible edema without infarction or haemorrhage do not qualify as stroke.

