12.7 Rules for putting enrolment on hold

If one of below mentioned criteria is fulfilled, enrolment of additional patients in the clinical trial program will be placed on hold. An urgent safety committee meeting will be scheduled to decide further actions. Dosing of patients on treatment may continue while further evaluation is made by the safety committee. A substantial amendment with relevant data must be submitted to the regulatory authorities to support restart of the trial.

- Significant thromboembolic event*
- Event of DIC
- Anaphylactic reaction related to trial drug administration
- Death of trial patient which may be related to the trial product
- Two or more other trial product related SAEs similar in nature have been reported and/or detected by laboratory measurements
- Trends in AEs, clinical observations or laboratory parameters which raise concerns about the safety of continued treatment

Protocol
 Trial ID:NN7415-4255
 UTN:U1111-1179-3872
 EudraCT no.:2016-000614-29

~~CONFIDENTIAL~~

Date:	05 May 2017	Novo Nordisk
Version:	2	
Status:	Final	
Page:	93 of 124	

* Superficial thrombophlebitis or venous thrombosis associated with indwelling catheters is not considered a significant thromboembolic event unless evaluated as such by the investigator

If two or more other trial product related SAEs similar in nature have been reported and/or detected by laboratory measurements, or if trends in AEs, clinical observations or laboratory parameters raise concerns about the safety of continued treatment, the safety committee (see section [12.8.1](#)) will then decide whether further dosing of any patients in the clinical trial program should be continued, paused or discontinued.

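### Section 12.1.6 files primary cerebral and subarachnoid haemorrhage under the thromboembolic AESI, although Table 8-3 treats intracranial bleeds as severe bleeding episodes

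*Protocol*

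**What the plan says.** All references are to protocol version 2. Version 1.0 has the same stroke text, so this is not a by-product of the amendment.

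- **Section 12.1.6** has a single AESI group, "Thromboembolic events including but not limited to", with stroke (D) as one item. Part D says the term "should be broadly used to include all of the following". The list has ischaemic and thrombotic entries and also haemorrhagic ones: "Definition of intracerebral haemorrhage: A focal collection of blood within the brain parenchyma or ventricular system that is not caused by trauma", silent cerebral haemorrhage, and subarachnoid haemorrhage. It closes with stroke not otherwise specified, which may be of either origin.
- **Section 8.3.1, Table 8-3** defines severe bleeding episodes: "Examples: intracranial, retroperitoneal, iliopsoas and internal neck bleeding episodes", among others. The same section says "Prophylactic treatment with concizumab should continue independent of bleeding episodes and their treatment", subject to the investigator's judgement. On reporting it says "Only report the bleeding episode as an AE/SAE if fatal, life threatening or evaluated as related to trial product", and 12.1.1 agrees.
- **Section 5.3.2** says that bleeding episodes classified as severe are recorded as serious adverse events.
- **Section 6.4**, criterion 5 for mandatory discontinuation, reads "Thromboembolic event".
- **Section 12.7** puts enrolment on hold for a "Significant thromboembolic event". Its footnote excludes only superficial thrombophlebitis and catheter-related venous thrombosis, unless the investigator judges otherwise.

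**The concern.** In severe haemophilia A, a non-traumatic bleed into the brain is the kind of event that prophylaxis is meant to prevent. Thromboembolism is the main potential risk that section 18.1 describes for this pro-coagulant drug. The two usually point in opposite directions for efficacy and benefit-risk. A definition that puts both under one thromboembolic label makes the AESI total ambiguous in a small trial, where one case is visible.

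There is also a question of conduct. The same patient can be described by the bleeding-episode rules and by the thromboembolic rules, and the protocol does not say which governs. If a site read 6.4(5) as covering the bleed, the patient would leave treatment and, under 8.1.4, the trial. Section 17.3 would then use only his data up to that point, assuming data are missing at random. If 12.7 were read the same way, enrolment across the programme would pause, and a substantial amendment would be needed to support restart.

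**Working it through.** The protocol gives no figure on this point to reproduce. The check is a tracing of text, followed by one small calculation of scale.

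**1. Which haemorrhages are inside the AESI?** Part D includes everything it lists.
- Intracerebral haemorrhage: included, non-traumatic only. The definition also takes in parenchymal haemorrhage after a CNS infarct.
- Silent cerebral haemorrhage: included, non-traumatic only.
- Subarachnoid haemorrhage: included. The base definition has no trauma exclusion; the related stroke definition does.
- Subdural and epidural bleeds: not listed.

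No sentence limits the AESI to ischaemic or thrombotic stroke. Part D opens by speaking only of CNS infarction, which suggests that a general stroke list was taken over whole.

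**2. Does such a bleed become an AESI?** Section 12.1.6 draws AESIs from adverse events, so the bleed must first be one.
- Under 5.3.2, a severe bleeding episode is recorded as a serious adverse event. Table 8-3 makes intracranial bleeds severe, so the condition is met.
- Under 8.3.1 and 12.1.1, it is met only if the bleed is fatal, threatens life or is judged related.

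The two routes disagree. Under either, a life-threatening listed haemorrhage becomes a thromboembolic AESI.

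**3. Does it reach 6.4(5) and 12.7?**
- For the link: 12.1.6 is the only place where the protocol defines thromboembolic events. The 12.7 footnote on superficial thrombophlebitis closely follows 12.1.6 F. Neither 6.4 nor 12.7 exempts haemorrhage.
- Against it: neither section cites 12.1.6. Both list DIC separately, whereas 12.1.6 puts DIC inside the thromboembolic group. Section 12.7 also requires the event to be significant.

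The link is a possible reading, not a stated rule.

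**4. Scale of one event.** Inputs: 33 patients to be dosed and 30 to complete (6.1); 76 weeks of treatment (5.3).
- Full exposure: 33 × 76 = 2,508 patient-weeks; 2,508 / 52.18 = 48.1 patient-years.
- Completers only: 30 × 76 = 2,280 patient-weeks; 2,280 / 52.18 = 43.7 patient-years.
- One event: 1/48.1 = 2.1 to 1/43.7 = 2.3 per 100 patient-years.
- Proportion: 1/33 = 3.0%. Exact 95% limits: lower 1 − 0.975^(1/33) = 0.08%; upper is the p solving P(X ≤ 1 | n = 33, p) = 0.025, which is 15.8%.

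**The case against.** **Broad capture may be deliberate.** Section 18.1 names bleeding from consumption of coagulation factors as a theoretical risk, and DIC may present with a bleeding tendency. A cerebral bleed on this drug could therefore reflect excess pharmacology, so close scrutiny of every stroke is defensible. That stands as a reason to keep all haemorrhages fully reported. It does not justify counting a primary haemorrhage as thromboembolic, and DIC already has its own definition, stop criterion and hold criterion.

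**The bleed would not be hidden.** Section 17.6.2 summarises treatment-emergent events by system organ class and preferred term and lists all adverse events. No thromboembolic rate is an endpoint. This also stands, and it limits the consequence to the AESI label and what follows from it.

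**Stronger readings that the protocol does not support.**
- A reader might infer that any intracranial bleed is a thromboembolic event. Part D mostly excludes trauma, omits subdural and epidural bleeds, and applies only once the bleed is an adverse event.
- A reader might infer that such a bleed automatically meets the stop and hold criteria. The missing cross-references, the separate listing of DIC and the requirement of significance leave this as an inference.
- A reader might infer that 8.3.1 and 6.4 give directly opposite orders. The default in 8.3.1 to continue dosing allows for the investigator's judgement, and 6.4 allows discretionary discontinuation for safety, so the conflict is weaker than that. The plainer contradiction is between 5.3.2 and 8.3.1 with 12.1.1, on whether a severe bleed is a serious adverse event.

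**Conclusion.** The classification problem is established from the text. Non-traumatic intracerebral and silent cerebral haemorrhage, and subarachnoid haemorrhage, fall within the thromboembolic AESI whenever they are reported as adverse events, while Table 8-3 puts intracranial bleeds among severe bleeding episodes.

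A single case is enough to change the AESI count visibly, by the amount computed above. The rate depends on the assumed exposure: the lower figure takes all 33 patients through 76 weeks, and the higher counts only the 30 planned completers. The consequences for 6.4(5) and 12.7 are conditional on reading those sections through 12.1.6.

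The primary endpoint model and the sample size are not affected, except indirectly if a patient were discontinued on this reading.

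**What to change.** **Definition and tabulation.** In 12.1.6 D, and wherever the AESI is tabulated, separate primary haemorrhagic events from ischaemic and thrombotic events. Keep haemorrhagic infarction, parenchymal haemorrhage after CNS infarction and haemorrhage from cerebral venous thrombosis with the thrombotic events, since their origin is ischaemic or thrombotic. State how stroke not otherwise specified is assigned. Report every haemorrhage in full, in its own row.

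**Reconciliation.** The sponsor must bring 5.3.2, 6.4, 8.3.1 with Table 8-3, 12.1.1, 12.1.6 and 12.7 into agreement on three points:
- whether a haemorrhagic stroke is a bleeding episode, an AESI or both;
- when a severe bleed is a serious adverse event;
- whether 6.4(5) and 12.7 use the 12.1.6 definition, and so whether such a bleed falls under them.

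Which clinical rule applies is for the sponsor to decide; none is proposed here.

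**Cost.** A wording amendment with cross-references. No new data are collected and none are lost.

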12.1.7 Technical complaints

A technical complaint is any written, electronic, or oral communication that alleges product (medicine or device) defects. The technical complaint may be associated with an AE, but does not concern the AE itself.

Examples of technical complaints:

- The physical or chemical appearance of trial products (e.g. discoloration, particles or contamination)
- All packaging material including labelling
- Problems related to devices (e.g. to the injection mechanism, dose setting mechanism, push button or interface between pen and needle)

